Official Title:	i-Matter: Investigating an mHealth Texting Tool for Embedding Patient-reported Data Into Diabetes Management
NCT Number:	NCT03652389
Study Number:	18-01044
Document Type:	Study Protocol and Statistical Analysis Plan
Date of the Document:	
January 22, 2021

CLINICAL STUDY PROTOCOL

i-Matter: Investigating an mHealth texting tool for embedding patient-reported data into diabetes management

Study Number

s18-01044

Sponsors

Agency for Healthcare Quality and Research

[name]

Merck & Co., Inc.

Kenilworth, NJ, United States

Protocol Version

January 5, 2021

version 10

Study Number s18-01044

March 17, 2020 - version 9

Study Personnel

Principal Investigator

[name]
New York University
Email: [contact]

Study Number s18-01044

March 17, 2020 - version 9

Synopsis

Primary Objective

To compare the efficacy of MJS DIABETES vs. usual care (UC) on HbA1c reduction at 12-months.

Secondary Objectives (if applicable)

1. To compare the efficacy of MJS DIABETES vs. UC on adherence to self-care behaviors.
2. To evaluate the potential mediators of the intervention effects (diabetes knowledge, self-efficacy, outcome expectation, and patient-provider communication) on adherence to self-care behaviors and HbA1c reduction.

Primary Outcome Variables

The primary outcome, mean reduction in levels of HbA1c, will be extracted from patients' medical records.

Secondary and Exploratory Outcome Variables (if applicable)

The secondary outcomes are: 1) adherence to self-care behaviors (assessed with the Summary of Diabetes Self-Care Activities questionnaire) and 2) the theoretical mediators

of capability (assessed with the diabetes knowledge scale), motivation (assessed with the diabetes self-efficacy and outcomes expectations scales) and opportunity (assessed with the Interpersonal Processes of Care survey).

Study Duration

The study duration is 5 years. The formative phase will be 12 months and the clinical efficacy trial will be the remaining 4 years. Participants enrolled in the clinical efficacy trial will participate in the trial for 12 months. The approximate start date for the trial is September 1, 2018 and the approximate end date is August 31, 2023.

Study Design

Using a mixed-methods design, the proposed study will be conducted in two phases: 1) A formative phase, based on user-centered design and 2) a clinical-efficacy phase.

For the formative phase, we will use a mixed methods observational design to refine the study intervention.

For the clinical efficacy phase, we will conduct a single-blinded, phase 3 randomized controlled trial.

Study Population

The study population will include primary care providers and patients with uncontrolled type 2 diabetes (T2D) receiving care in the network of Family Health Centers (FHCs) and Faculty Group Practices (FGPs) at NYU Langone Health.

PCP Eligibility Criteria

Inclusion Criteria: (a) Fulltime primary care provider (MD/DO, NP) practicing at the participating FHC and/or FGPs and (b) provides care to at least five patients with a diagnosis of T2D.

Exclusion Criteria: Refuse to participate

Patient Eligibility Criteria

Inclusion Criteria:

- Have a diagnosis of T2D for ≥ 6 months;
- Have uncontrolled T2D defined as HbA1c $> 7\%$ documented in the EHR on at least two visits in the past year;
- Fluency in English or Spanish;
- Be willing to send/receive text messages; and
- Be > 18 years of age.

Exclusion Criteria:

- Refuse or are unable to provide informed consent;
- Have acute renal failure, end stage renal disease (ESRD) or evidence of dialysis, renal transplantation, or other ESRD-related services documented in the electronic health record (EHR);
- Have significant psychiatric comorbidity or reports of substance abuse (as documented in the EHR);
- Are pregnant or planning to become pregnant within 12 months;
- Currently participate in another T2D study; or
- Plan to discontinue care at the clinic within the next 12 months.

Number of Participants

Formative Phase

Patients: 36 patients with uncontrolled T2D

Providers: 14 primary care providers

Clinical Efficacy Trial [Sample includes new participants that did not participate in the formative phase]

Patients: 282 patients with uncontrolled T2D

Study Number s18-01044

March 17, 2020 - version 9

Providers:14 primary care providers

Abbreviations

Abbreviation	Explanation
AHRQ	Agency for Healthcare Research and Quality
DSMP	Data Safety Monitoring Plan
EHR	Electronic Health Record
HbA1c	Hemoglobin A1c
mHealth	Mobile Health
MJS	Modern Journal System
NP	Nurse Practitioner

PCP	Primary Care Provider
PHI	Personal health information
PI	Principal Investigator
PRO	Patient-reported outcome
RCT	Randomized controlled trial
SMBG	Self-monitoring blood glucose
T2D	Type 2 diabetes
TAM3	Technology Acceptance Model-version 3
UC	Usual Care
UCD	User-centered design

Study Number s18-01044

1.1 Introductory Statement

This document is a protocol for a human research study. The purpose of this protocol is to ensure that this study is to be conducted according to ICH GCP guidelines (CRF 21 Part 312), applicable government regulations and Institutional research policies and procedures.

2 - Background

2.1 Background/prevalence of research topic

Although the prevalence of type 2 diabetes [T2D] has remained steady in recent years, T2D remains a significant cause of morbidity and mortality, particularly in vulnerable populations who continue to suffer disproportionately higher rates of complications. For example, only 53% of patients with T2D meet American Diabetes Association hemoglobin A1c (HbA1c) target of <7%. The number of patients who fail to meet this target is even higher in safety-net primary care practices - a place where most vulnerable populations receive their care. To date, the care of patients with T2D has focused largely on patient self-management (adoption of healthy lifestyle, medication adherence) and the use of clinical parameters such as HbA1c levels to determine treatment effectiveness. Although several meta-analyses support the link between improvements in patient self-management and reduction in HbA1c, their effect sizes are modest at best (-0.43% reduction in HbA1c), particularly among vulnerable populations (only -0.31% reduction in HbA1c).

3 - Rationale/Significance

3.1 Problem Statement

A major limitation of the current type 2 diabetes literature is the lack of focus on patients' perspectives of the physical and psychosocial impact of T2D on their daily lives as well as their ability to manage the disease and adhere to the recommended treatment regimen. Importantly, psychosocial factors (e.g., distress), which are not often captured in clinical practice, are of utmost importance to T2D patients' health behaviors. Measures of patient-reported outcomes (PROs) are a standardized and quantifiable approach that allows the collection and integration of data on patients' perspective into the clinical management of T2D. Despite the central role PROs play on T2D patients' ability to manage their disease, PCPs overestimate how frequently they assess PROs in the clinic visit, as compared to patients (76% vs. 55%, respectively). However, if we are to make an impact on the growing burden of T2D on patients and the broader society, treatment strategies must seek to balance primary care providers' (PCP) pursuit of glycemic control against patients' emotional, physical, and social experiences with their disease. In order to be successful such strategies must possess the following qualities: 1) provide data that is actionable by primary care providers (PCPs); 2) support patient engagement in their care both within and outside the practice; 3) improve clinical outcomes; and 4) be integrated within the clinic workflow, as part of the electronic health record (EHR). Practice-based trials that evaluate the efficacy of integrating PROs into the care of T2D patients in safety-net primary care

practices, is at its embryonic stage.

3.2 Purpose of Study/Potential Impact

Although achieving glycemic control is of clinical importance, it is the daily experiences of living with T2D that drive patients' decisions to adhere to treatment recommendations and become engaged in their care. Even with the most efficacious treatments, failure to incorporate patients' perspective of their disease into clinical decision-making will make achieving the outcomes desired by patients and PCPs unattainable. Thus, an ideal opportunity to improve patient outcomes is being missed in primary care practices, especially among vulnerable populations who suffer disproportionately higher rates of complications. To date, PROs have been associated with improvements in quality of life, better patient-provider communication, and reduced emergency department visits among patients with chronic diseases. Despite these benefits, practice-based studies that incorporate PROs into diabetes care have lacked patient and PCP involvement in their development thus, they fail to meet the unique needs and preferences of patients, and lack the technical infrastructure to support their integration into the clinic workflow, greatly limiting their impact. If successful, this study will lay the foundation for developing a disseminable strategy for improving clinical and functional outcomes in patients with T2D. Specifically, this study will provide much needed evidence in three vital areas: 1) the facilitators and barriers to using mHealth platforms to record and track PROs for diabetes management; 2) the conditions under which mHealth interventions 'work' in primary care settings and the

organizational, individual and technical factors that are required to support their use; and 3) the theoretical drivers that underlie mHealth interventions to improve outcomes. These results should have important population health value for patients, providers, healthcare systems and policy makers by identifying the optimal set of tools and procedures to effectively collect and monitor PROs in patients' daily lives and as part of routine clinical care.

3.3.1 Potential Benefits

The intervention is expected to benefit the patients by improving adherence to self-care behaviors, reducing their cardiovascular risk profile, increasing their role as active participants in the management of their health, and potentially improving their diabetes control. The intervention is expected to benefit PCPs by improving communication with their patients helping to inform treatment-decisions for effective management of T2D. The knowledge gained from this study will also provide key academic, community, and policy stakeholders a patient-centered intervention approach for chronic disease management that has potential for broad dissemination, ultimately contributing to a reduction in the burden of T2D in vulnerable populations and the broader society.

3.3.2 Potential Risks

Though we expect the level of risk due to this project to be minimal, potential risks may include the following:

Violation of participant privacy and confidentiality: There is a potential risk to the PCPs and

patients with regards to violations of privacy and confidentiality, since text messages, emails, and recordings of interviews, focus groups, and real patient-PCP clinic visits will be used as a source of data. To mitigate this issue, all recorded sessions will be conducted in a private room in the FHC or FGP. Also, when sending recruitment information by email: Send Safe secure email will be used to contact patients. NYU Langone does not permit sending any patient health information via unencrypted email.

Privacy and Security Protections for Participants: To mitigate any breaches in security or privacy as it relates to the Modern Journal System (MJS) DIABETES intervention, we will adhere to policies by the Federal Office of the National Coordinator for Health IT as well as the principles of the Markle Framework for Networked Personal Health Information and the technical specifications of the O-Auth protocol for user authentication. Based on these sources, the Privacy and Security Plan will include:

- Development of explicit policies governing the access to individual PRO data in the MJS intervention (e.g., limited to study staff who require it for authorized, legitimate, and documented purposes)
- A firm policy prohibiting the study staff or consultants (i.e., Rip Road, [name]) from access to individual patient health records, except for specific purposes of research approved by the IRB
- Encryption of all sensitive user data within the MJS mobile platform and EHR interface to prevent unauthorized access and disclosure in the case of a physical

Study Number s18-01044

March 17, 2020 - version 9

loss. No personal health information (PHI) will be collected through the MJS platform.

- Regular training and reminders sent to study staff and consultants about system security and the need to follow related protocols to protect the confidentiality of user information. Policies will also be established for handling violations to security protocols, if they arise.
- A protocol outlining regular risk assessments and system audits to ensure a secure transmission of patients' data, including use of encryption protocols such as Secure Socket Layer (SSL) technology. The inclusion of [name] as a co-I on the proposal will ensure that these Privacy and Security guidelines are in accord with norms and existing practices within the clinic.

Protections against Violations of Confidentiality: As part of the process involved in obtaining written informed consent, all patients/PCPs will be reminded that their responses are confidential and that they may refuse to participate in the project or withdraw at any time without explanation, and further, that such an action will in no way affect their future interactions with the FHC and/or FGP. To ensure confidentiality, data will be associated with an individual participant only by an assigned identification number, the code for which will be kept in a locked drawer. Only members of the research team will have access to the participants' personal information file. All computers containing confidential data will meet security requirements established by the HIPAA Security Rules, and established by the Office of Management and Budget (OMB) in OMB Circular No. A-120, Appendix III.

Office of Management and Budget (OMB) in OMB Circular No. A-130, Appendix III - Security of Federal Automated Information Systems. Specifically, all electronic interview data will be saved on a secure server housed by NYULMC and backed up daily or weekly depending upon the receipt of data. PHI will be confined to a secure server that is not connected to the Internet. All computers will be password protected and on a private LAN network. No file and database servers are accessible to the public through the Internet. Prior to inclusion in any data set (internal and external), data will be stripped of all identifying information.

Since text messages will be transmitted in this study, a variety of measures will be used to reduce information security risk. Patients' text responses will be securely handled via Rip Road's HIPAA compliant hardware infrastructure. Rip Road follows a set of well-developed policies and procedures vetted by top healthcare organizations in the management and protection of all data tracked through MJS. Patient information will be de-identified for administrative views and for analysis within the Rip Road system. Text messages will not identify patients as having a specific disease or include any PHI information such as patients' name. Patients will be informed that their data are stored, without identifiers, in the highly secure HIPAA-compliant Cloud. They also will be informed that there is a remote possibility that the Cloud or their mobile account could be hacked and that information about study activities (communications, recorded behaviors) could be disclosed. However, these data are not sensitive in nature. Devices will be configured with a participant ID and no other personal identifiers. It is possible that a participant could lose their mobile phone or leave it in a public location with the screen turned- on, enabling others to view personal information.

Study Number s18-01044

March 17, 2020 - version 9

To address this, we will assist the participant in enabling a screen saver that is activated when the mobile phone has been idle for 5 minutes, as well as a 4-digit password that must be entered each time the device is turned-on. They will also be instructed on how they can turn off home screen notifications if they choose to. Finally, all study staff will be trained in the NYULMC Research Practice Fundamentals, which include training in issues of confidentiality and requires trainees to sign a confidentiality agreement.

Anxiety: There is a potential risk that participants (PCPs and patients) may feel anxious during the audiotaped sessions. To mitigate this issue, the research assistant (RA) who collects the data will be trained to act professionally and address all patients' concerns. Participants will also be informed that they do not need to answer any questions that they are not comfortable with. To insure privacy during the completion of study measures, participants will complete questionnaires in a room with the door closed. In regards to the taped sessions, PCPs/patients will be reminded that the tapes are only for research purposes and will not influence their relationship with the FHC and/or FGP. Moreover, they will be reassured that the tapes will be saved in a secure and confidential database that only the study staff will have access to, and that have the right to ask that the tapes be deleted if they feel sensitive information was discussed during the sessions that they do not want the research team to hear.

Hyper- or hypoglycemia: Since this study is recruiting patients with uncontrolled T2D, occasionally someone may have low blood sugar or high blood sugar during their study participation. All patients will have a PCP as part of this study; however, it is quite

conceivable that a patient reports blood glucose data that will require more aggressive management. When problems arise suggesting the need to re-evaluate the medication regimen, participants will be referred to their provider of record, or local emergency room as appropriate.

Study Number s18-01044

March 17, 2020 - version 9

4 - Study Objectives

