11.	Communication: 2-item survey assesses the whether the users communication with healthcare provider improved after using tool
12.	Behavior Intention of use: 4-item survey that assesses the likelihood of using the tool within a specific time frame

Description of MJS DIABETES intervention (Phase 2)

Study Number s18-01044

March 17, 2020 - version 9

Phase 2 of the study will not begin until all materials for this phase have been fully developed. These materials will then be submitted to the IRB via a modification for review and approval.

Patient intervention: MJS DIABETES is comprised of 5 components: 1) PRO assessments, sent via text message; 2) adherence text message assessments; 3) data-driven feedback text messages 4) motivational text messages; and 5) journal reports that visually display PRO data.

MJS helps patients (and their provider) see how their diabetes symptoms and psychosocial functioning are changing overtime. Participants who enroll in the study agree to have messages sent to their phone based on one of several PRO categories. These include: (1) diabetes quality of life; (2) overall emotional health; (3) lifestyle behaviors; (4) medication adherence; and (5) physical functioning. PRO questions will be sent on a daily or weekly basis, depending on the PRO (i.e., adherence is a daily measure while quality of life is sent on a weekly basis). The list of potential PROs that will be sent to patients over the course of the 12-month study and their primary questionnaire source are shown in the Table below. No PHI will be collected in the MJS DIABETES tool. All data is a numerical response that is anonymous.

Potential MJS PROs	Scaling	Source
Over the past week, how would you rate your level of fatigue because of your diabetes?	0 (not at all tired)-10 (extremely tired) scale	Global Health PROMIS Tool
How would you rate your sleep quality over the past 7 days?	0 (very poor)-10	NIH PROMIS Sleep

	(excellent) scale	Quality
Over the past week, how often were you able to take your diabetes medication on time?	Never Rarely Sometimes Often Always	Diabetes self-management questionnaire
How many of the last seven days have you followed a healthful eating plan for diabetics?	0-7 days	Summary of Diabetes Self-Care Activities
In general, my present quality of life is	As good as it can be Good Quite good Neither good or bad Quite bad Bad As bad as it could possibly be	Audit of Diabetes Dependent Quality of Life

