Over the past week, how often were you been bothered by emotional problems such as feeling anxious, depressed or irritable because of your diabetes?	Never Rarely Sometimes Often Always	Global Health PROMIS Tool
Over the past week, what percent of the time did you take all your diabetes medications as your doctor prescribed?	0-100%	Self-Rating Scale Item
On how many of the last seven days did you take the correct number of (pills/injections) for this medication?	0-7 days	Summary of Diabetes Self-Care Activities
Over the past week, how often did you eat [favorite unhealthy food]?	Always Often Sometimes Rarely Never	Perceived Dietary Adherence Questionnaire

Study Number s18-01044

March 17, 2020 - version 9

On how many of the past 7 days did you eat lots of sweets or other foods rich in carbohydrates?	0-7 days	Perceived Dietary Adherence Questionnaire
How effective are you in coping with your diabetes?	1 (not at all) to 5 (extremely effective)	Appraisal of Diabetes Scale
How many times over the past week did you eat desserts like cookies, cakes and muffins or other sweets? Do not include sugar free kinds.	Never 1 time 2-3 times 4 or more times	NHANES Dietary Screener Questionnaire
How many times over the past week did you refined carbohydrates like white bread, white flour tortillas, dinner rolls and bagels?	Never 1 time 2-3 times 4 or more times	NHANES Dietary Screener Questionnaire
On how many of the past 7 days did you space carbohydrates evenly throughout the day?	0-7 days	Perceived Dietary Adherence Questionnaire
Over the past week how well could you control your emotions?	Not at all Poorly Fairly well Very well Extremely well	Thrive Questionnaire
In general, how would you rate your mental health, including your mood and your ability to think?	Poor Fair Good Very good Excellent	Global Health PROMIS Tool
How much was the quality of life of your life affected by the time required to control your diabetes?	0 (Not at all affected) – 10 (as bad as I can be)	Patient-reported outcome-Quality of Life
Over the last week, did you experience any weight gain because of your diabetes	Always Often	Diabetes Impact Measurement Scales

	Sometimes Rarely Never	
Over the last week, did you feel irritable or moody because of your diabetes	Always Often Sometimes Rarely Never	Diabetes Impact Measurement Scales

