7.3 Subject Confidentiality

As part of the process involved in obtaining written informed consent, all patients/PCPs will be reminded that their responses are confidential and that they may refuse to participate in

Study Number s18-01044

March 17, 2020 - version 9

the project or withdraw at any time without explanation, and further, that such an action will in no way affect their future interactions with the FHC or FGP. To ensure confidentiality, data will be associated with an individual participant only by an assigned identification number, the code for which will be kept in a locked drawer. Only members of the research team will have access to the participants' personal information file. All computers containing confidential data will meet security requirements established by the HIPAA Security Rules, and established by the Office of Management and Budget (OMB) in OMB Circular No. A-130, Appendix III - Security of Federal Automated Information Systems. Specifically, all electronic interview data will be saved on a secure server housed by NYULMC and backed up daily or weekly depending upon the receipt of data. PHI will be confined to a secure server that is not connected to the Internet. All computers will be password protected and on a private LAN network. No file and database servers are accessible to the public through the Internet. Prior to inclusion in any data set (internal and external), data will be stripped of all identifying information.

Since text messages will be transmitted in this study, a variety of measures will be used to reduce information security risk. Patients' text responses will be securely handled via Rip Road's HIPAA compliant hardware infrastructure. Rip Road follows a set of well-developed policies and procedures vetted by top healthcare organizations in the management and protection of all data tracked through MJS. Patient information will be de-identified for administrative views and for analysis within the Rip Road system. Text messages will not identify patients as having a specific disease or include any PHI such as patients' name.

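### Sections 3.3.2 and 7.3 promise that texts will not reveal a disease, but 9 of the 19 candidate text questions in 6.1.1 name diabetes

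*Combined protocol and SAP*

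**What the plan says.** Section 3.3.2 puts privacy and confidentiality first among the potential risks and names text messages as one source of that risk. Among the measures it lists is this sentence: "Text messages will not identify patients as having a specific disease or include any PHI information". Section 7.3 says the same: "Text messages will not identify patients as having a specific disease or include any PHI such as patients' name".

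Section 6.1.1 says that the patient-reported outcome (PRO) assessments go out by text message, and it tables potential questions to be sent over the 12 months. One asks "how would you rate your level of fatigue because of your diabetes". Another asks "what percent of the time did you take all your diabetes medications as your doctor prescribed".

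Section 3.3.2 also foresees a phone being lost or left in public with its screen on. Its answer to that case is a screen saver after 5 idle minutes, a 4-digit password, and instruction on switching off home-screen notifications for patients who want this. Sections 5.1 and 6.1.1 both say that Phase 2 will not start until its materials are developed and submitted to the IRB.

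**The concern.** The promise is about what a message says. The screen lock, the password and the notification setting limit who sees a message, but they do not change its words. If a text about the patient's diabetes is on display, only a neutral wording would keep the diagnosis private, and the promise is that the wording will be neutral.

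Two things are at stake. One is the accuracy of a participant-protection statement that the protocol makes twice. The other is that a patient told this would have less reason to change the notification setting, which section 3.3.2 leaves to choice.

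**Working it through.** The documents give no count to reproduce, so the check is a direct count of the table in section 6.1.1, followed by a reading of the promise against it.

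**Count.** The table lists 19 questions. In table order, those that name the disease are:

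| Item | Topic | Reference to the disease |
|---|---|---|
| 1 | Fatigue | attributed to the patient's diabetes |
| 3 | Medication taken on time | the patient's diabetes medication |
| 4 | Eating plan | for diabetics |
| 6 | Emotional problems | attributed to the patient's diabetes |
| 7 | Percent of time medication taken | the patient's diabetes medications |
| 11 | Coping | with the patient's diabetes |
| 17 | Quality of life and time burden | controlling the patient's diabetes |
| 18 | Weight gain | attributed to the patient's diabetes |
| 19 | Irritability | attributed to the patient's diabetes |

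That is 9 of 19, and 9 / 19 = 47%. Eight of the nine address the reader directly (your diabetes); item 4 says diabetics. The other 19 − 9 = 10 do not name the disease. Neither do the sample feedback and motivational texts in the same section.

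**Reading the promise.** The sentence makes two promises: no specific disease, and no protected health information such as a name. Only the first is contradicted, since no listed question carries a patient's name. The first promise has no exception, so one retained item out of the nine is enough to break it.

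**How many such texts a patient would get.** This cannot be derived, because the documents give neither the final items nor their schedule. Section 6.1.1 says some PROs are daily and some weekly; section 6.3.1 gives a ceiling of 3 texts a day, or 3 × 365 = 1,095 a year. Under stated assumptions:

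- none of the nine selected: 0 a year
- one selected and sent weekly: 1 × 52 = 52 a year
- all nine sent weekly: 9 × 52 = 468 a year, which is below the ceiling

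The range shows only that the number depends on a selection not yet made. The conclusion does not rest on it.

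**The case against.** **The list is provisional.** This stands. The table is headed as potential PROs and looks like a candidate pool: items 3, 7 and 8 all ask about taking medication, and items 6 and 19 both ask about irritability. Final wording may differ. The promise is nevertheless in the current text, beside questions that break it, and a list not yet final is a reason to settle the wording now.

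**To identify a patient takes a name.** This does not stand. The sentence treats disease and name as separate promises. A text about the reader's diabetes, sent to a mobile number verified at opt-in, discloses the disease to anyone who knows whose phone it is.

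**The data are numerical and anonymous.** Section 6.1.1 says this of the replies. The disclosure lies in the outgoing question.

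**The sentence is one measure among many.** This stands. Encryption, de-identification, ID-only records and HIPAA-compliant hosting are not put in doubt, and the screen-on case has its own controls.

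**Rewording is not free.** This stands for the questions that ask about something because of diabetes. Replacing the disease with a general health condition changes the attribution in items drawn from named instruments, in patients whose comorbidity the trial expects and measures. Section 6.4.3.2 relates change in PROs to change in the outcomes, and the replies feed the reports to primary care providers.

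**Conclusion.** The point holds as an inconsistency to be corrected. An unqualified privacy statement, made in sections 3.3.2 and 7.3, conflicts with 9 of the 19 candidate questions in section 6.1.1 and fails if any one of them is sent. This rests on the table as printed and on the ordinary meaning of the sentence. It does not touch power, type I error or the HbA1c analysis.

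Four stronger readings are tempting, and the documents do not support them:

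- A reader might infer that the privacy protection as a whole is already failing for every intervention patient. The list is provisional, ten listed questions do not name the disease, and the other controls stand.
- A reader might multiply 1,095 by 9/19 and report about 519 disclosing texts per patient. That assumes the maximum of 3 texts every day, use of all 19 items and equal frequency, none of which the documents state.
- A reader might say that the IRB's judgement of risk rests on the promise. Nothing in the documents says what the IRB relied on, and it is still to review the Phase 2 materials.
- A reader might hold the mood questions against the statement "However, these data are not sensitive in nature". In section 3.3.2 that statement follows the possibility of hacking, for data stored without identifiers. It is not about someone reading a phone screen.

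**What to change.** Before the Phase 2 materials go to the IRB, do one of the following.

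**Preferred: correct the promise.** In sections 3.3.2 and 7.3, say that texts may refer to diabetes but will not include the patient's name. Check the consent form and the Mobile Terms and Conditions, neither of which is available here, and correct them if they repeat the promise. Make hiding message previews on the lock screen a routine step of the one-to-one training already planned in Table 6, with patients free to decline. The cost is an edit in two sections, possibly in patient-facing text, and a short addition to the training. The question wording stays as in the source instruments.

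**Alternative: keep the promise and change the questions.** Remove the disease name where the meaning survives, for example 'your medication' (items 3 and 7) or 'your eating plan' (item 4). For items 3 and 7, the training should make clear which medication is meant, since patients may take others. The cost is some departure from source wording. It matters most for items 1, 6, 18 and 19, which ask about something because of diabetes; items 11 and 17 also lose their object if the disease is removed. Any of these six kept as worded would still break the promise, so this route works only if they are dropped or suitably reworded. The self-care outcome would not be affected, because it is measured by a separately administered questionnaire.
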